### **Missing data**

The frequency of missing values for each variable will be collected and reported as necessary. If there are missing values for the primary or secondary outcome variables, individual patients will be excluded from the analysis of the respective outcome and results will be reported for cases with available outcome information.

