### Study Procedures

Prior to randomisation, if subjects are eligible based on inclusion/exclusion criteria, informed consent will be obtained from participants. Once informed consent is obtained, the following information will be collected from the subject's medical record: demographics, past medical/surgical history, preadmission medication list, severity of illness at time of admission, blood pressure, aspartate aminotransferase, alanine aminotransferase creatinine, troponin, cortisol level.

The study drug or placebo will be selected based on the randomisation scheme and prepared by investigational pharmacists. All study personnel will be blinded, except the investigational pharmacist, to the treatment group of the subject. Subjects will be randomised to receive either 20 mg PO every 8 hours of midodrine, or placebo PO every 8 hours.

The study drug will be delivered in a double-blinded manner until:

- ICU discharge
- Rate of phenylephrine exceeds 100 mcg/min, or rate of norepinephrine exceeds 8 mcg/min, or rate of metaraminol exceeds 60mcg/min
- Subject exhibits signs and symptoms of organ failure or hypoperfusion
- Serious allergic adverse event related to midodrine
- Epinephrine requirement
- Death

If the blood pressure goal is met for more than 24 hours without IV vasopressors and the attending physician determines that the study drug is no longer required, the study drug may be discontinued at the discretion of the treating physician.

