### Adverse Event Reporting

Our patient population is by definition critically ill in the ICU. It is expected that they will have a number of unrelated adverse health events (AE) during the course of their hospital stay. Therefore, we will limit the scope of our AE monitoring and recording to the following:

- Serious Adverse Events, defined as
  - Death, believed to be related to the study drug, or a death that is unexpected considering the acuity of a patient
  - A life-threatening experience believed to be related to the study drug
  - Persistent or significant disability or incapacity that is of greater frequency or severity than what would be normally expected in the course of critical illness
  - An event that jeopardises the Human Subject and may require medical or surgical treatment to prevent one of the preceding outcomes and is not expected in the course of critical illness
- Adverse Events possibly related to the study procedures are pre-specified in the list below:
  - Hypertension
  - Bradycardia
  - Hemodynamically significant tachyarrhythmia
  - New organ failure

Evidence for adverse events related to midodrine will be assessed until completion of all study measurements. They will also be included in the FDA Annual Progress Report.

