## STATISTICAL ANALYSIS PLAN

### Study aims

This randomised, controlled clinical trial evaluates the effect of oral midodrine versus placebo on time to liberation from intravenous vasopressors in ICU patients with refractory hypotension. The aim of this study is to assess the effects of midodrine treatment in patients otherwise ready for discharge from the ICU. The primary hypothesis is that midodrine treatment shortens the duration of receiving IV vasopressors compared to placebo.

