### Outcomes

- *Primary endpoint:*
  - Time until discontinuation of IV vasopressors, measured in hours from initiation of midodrine until discontinuation of IV vasopressors
- *Secondary endpoints:*
  - Time to ICU discharge readiness, defined as the number of days from study drug initiation to meeting discharge criteria
  - ICU length of stay, defined as the number of days in the ICU prior to transfer to the general floor
  - Hospital length of stay, defined as the total number of days in the hospital after first study drug administration
  - Rates of ICU readmission, defined as the number of patients readmitted back to the ICU after prior discharge to the general floor
- *Safety endpoints:*
  - Hypertension (increase in blood pressure to a systolic blood pressure (SBP) 20 percent higher than the predefined goal set by the primary team), bradycardia (decrease in heart rate 20 percent lower than the predefined goal set by the primary team), hemodynamically significant tachyarrhythmia (>20 percent decrease in systolic blood pressure).

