### Data Collection

Baseline descriptive data collection will occur on day of enrolment and includes age, sex, ethnicity, APACHE II score, admission diagnosis, pre-existing co-morbidities (diabetes, coronary artery disease, asthma, peripheral vascular disease, renal failure, psychiatric disease, musculoskeletal disease, and others) obtained from the subject, the subject's family, and the subject's medical chart. Baseline laboratory data will be recorded (haemoglobin, white cell count, alanine aminotransferase (ALT), international normalised ratio (INR), bilirubin, urea, creatinine, troponin, lactate). During the study daily SOFA scores, blood pressure goals, total fluid balances, transfused red blood cell units, administered corticosteroids, use of epidural analgesia, vasopressor and study drug start and end

times will be recorded. Days between admission and discharge from the ICU and hospital will be recorded. Readmissions to the ICU during the hospital stay will be identified through daily medical record review.

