### **Statistical analysis**

The study analysis will be performed on a modified intention-to-treat basis: All patients who were randomised and received at least 1 dose of the study medication will be included in the analysis.

Baseline and demographic characteristics will be presented using descriptive statistics. Continuous data will be expressed as means and standard deviations, or medians and interquartile ranges (IQR), depending on variable distribution. The normality of variable distribution will be assessed by exploratory data analysis, including histograms and boxplots. Differences in continuous data between groups will be assessed using a parametric t-test or Mann-Whitney U test, as appropriate. Categorical data will be presented as frequencies and proportions and analysed using a Chi-square test. If expected cell counts are small (less than 5), Fisher's exact test will be used instead. For all analyses, a two-sided p-value of less than 0.05 will be considered statistically significant. All analyses will be conducted under the supervision of a statistician blinded to intervention group assignment. Experienced study staff will perform data analysis in collaboration with biostatisticians using statistical Stata version 13 (StataCorp LLC, College Station, TX) or later.

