#### *Analysis of primary and secondary outcomes*

A parametric t-test or Mann-Whitney U test will be used, as appropriate, to determine whether time from initiation of midodrine until discontinuation of IV vasopressors, time from ICU admission to ICU discharge readiness, and ICU and hospital LOS differ between groups.

A Chi-Square or Fisher's exact test will be used to test whether rates of ICU readmission and incidence of adverse events are different between treatment groups.

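### The plan gives no primary-outcome value to a patient who dies on, or never comes off, IV vasopressors; its only rule for an absent outcome, exclusion, can bias the comparison if such failures differ between arms

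*Combined protocol and SAP*

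**What the plan says.** - **Endpoint.** The SAP's Outcomes section defines it as "Time until discontinuation of IV vasopressors, measured in hours from initiation of midodrine until discontinuation of IV vasopressors"; the protocol's Outcomes section agrees. Study aims speaks of "time to liberation from intravenous vasopressors in ICU patients with refractory hypotension".
- **Test.** Under Analysis of primary and secondary outcomes: "A parametric t-test or Mann-Whitney U test will be used, as appropriate". Either test needs one number, or at least one rank, per patient.
- **Analysis set.** Under Statistical analysis: "All patients who were randomised and received at least 1 dose of the study medication will be included in the analysis".
- **Absent outcomes.** Under Missing data: "individual patients will be excluded from the analysis of the respective outcome and results will be reported for cases with available outcome information". Counts of missing values are to be reported only where judged necessary.
- **Deterioration is foreseen.** Among the events in the protocol's Study Procedures that end study drug are death and "Subject exhibits signs and symptoms of organ failure or hypoperfusion". No outcome rule is attached to any of them.
- **Recording.** Data Collection lists "use of epidural analgesia, vasopressor and study drug start and end" times. It does not say how an infusion that ends because the patient died is to be classed, or whether vasopressor times are still recorded after study drug stops.
- **Deaths.** All-cause mortality is not an endpoint. Adverse Event Reporting limits recorded deaths to "Death, believed to be related to the study drug, or a death that is unexpected considering the acuity of a patient".

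**The concern.** Two kinds of dosed patient have no time to discontinuation: those who die while on vasopressors, and those alive who never come off them. I call both failures. A patient whose infusion is escalated and who later weans has a valid time and is not affected.

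If failures are treated as missing, they drop out of the primary analysis. That selects on an event after randomisation which treatment may affect, so randomisation no longer protects the comparison. If failures are mostly slow weaners, removing them makes the arm with more failures look faster. Where midodrine has fewer failures, the same mechanism hides part of a true benefit.

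The SAP never says that death is a missing value, so a second reading is open: the infusion end time at death could be entered as a discontinuation. That would score death as success. It fits poorly with the idea of liberation in the Study aims, and it offers nothing for patients alive on vasopressors.

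**Working it through.** **1. What each patient contributes.**

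| Patient | Time available? | Rule in the plan |
|---|---|---|
| Weans, with or without earlier escalation | Yes | Compared by t-test or Mann-Whitney |
| Dies on vasopressors | No, unless the stop at death counts | None specific; exclusion if treated as missing |
| Alive, never off vasopressors | No | None specific; exclusion if treated as missing |

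No section gives a censoring rule, a rank, a competing-event method or a follow-up horizon.

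**2. The plan's own figure.** Sample size estimation claims more than 80% power with 50 per group for 6 h, from a median of 17 h (0.38 × 17 = 6.46 h). No SD in hours is given, so this cannot be reproduced. Solved backwards: SD = 6 / [(1.960 + 0.842) × √(2/50)] = 6 / 0.560 = 10.7 h (10.6 h with the t distribution, d = 0.566). I use this only to set a range of spread. For a lognormal time with median 17 h, SD = 17 × exp(s²/2) × √(exp(s²) − 1):
- s = 0.51: 17 × 1.139 × 0.545 = 10.6 h, the spread implied by the plan
- s = 0.75: 17 × 1.325 × 0.869 = 19.6 h
- s = 1: 17 × 1.649 × 1.311 = about 37 h

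**3. Hand check of the shift.** If the failures were exactly the slowest fraction f, the median of those left would be 17 × exp(s × z((1 − f)/2)), with z(0.475) = −0.063 and z(0.425) = −0.189. For 15% against 5% failures:
- s = 0.51: 15.4 against 16.5 h, a shift of about −1.0 h
- s = 1: 14.1 against 16.0 h, a shift of −1.9 h

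These are upper limits. Simulation with the looser link in step 4 gave −0.7 to −1.0 h and −1.2 to −1.9 h.

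**4. Simulation, no effect on latent weaning time.** Assumptions: 60 per arm; T = 17·exp(sZ); failure when ρZ + √(1 − ρ²)·noise exceeds the normal quantile for the failure rate; two-sided 0.05; 6,000 to 8,000 trials per scenario. With failures excluded, the arm with more failures wins falsely (nominal 2.5%) as follows:

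| Failures | Patients per 60 | ρ | Mann-Whitney | t-test |
|---|---|---|---|---|
| Equal rates | – | 0.5–0.8 | 2.3–2.5% | – |
| Unequal | – | 0 | 2.1–2.7% | – |
| 10% vs 5% | 6 vs 3 | 0.5–0.8 | 3.6–5.7% | 3.8–6.6% |
| 15% vs 5% | 9 vs 3 | 0.5–0.8 | 5.9–10.8% | 5.5–13.8% |

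A variant with s = 0.8 and the chance of failure proportional to latent time gave 7.1% and a shift of about −1.0 h at 15% against 5%, and 2.6–3.4% per side at equal rates.

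**5. Power with a true 11 h against 17 h** (Mann-Whitney, 60 per arm, ρ 0.5–0.8). The last two columns have 5% failures on midodrine and 15% on placebo.

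| s | Exclusion, 5% both arms | Worst rank, 5% both arms | Exclusion, 5% vs 15% | Worst rank, 5% vs 15% |
|---|---|---|---|---|
| 0.51 | >99% | 98–99% | 98% | 99% |
| 0.75 | 86–89% | 80–84% | 70–75% | 88–90% |
| 1 | 63–67% | 56–59% | 38–45% | 66–72% |

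The loss under exclusion is 1 to 2 points at s = 0.51. At s = 1 it is 63 − 38 = 25 and 67 − 45 = 22 points, comparing like ends of the ranges; opposite ends give 18 to 29. Part of the worst-rank power at 5% against 15% comes from the failure difference itself.

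**The case against.** The strongest reply is that failures should be rare. Subject Selection caps vasopressor rates and excludes inadequate tissue oxygenation, and the Purpose and Study aims describe patients fit to leave the ICU apart from their hypotension. At the spread implied by the sample size section, the power loss is trivial. The supervising statistician is blinded, which limits a choice made to suit the result. All of this stands. It bears on the likely size; it neither supplies the missing rule nor removes the selection.

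Several stronger readings are tempting and not supported:

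- **That an inert drug would win too often.** The false-win rates assume no effect on latent weaning time but unequal true failure rates. A drug that did nothing would leave failure rates equal, and the rate then stays near nominal, chance imbalance included.
- **That the SAP contradicts itself.** A general analysis set followed by an outcome-specific exception is common. Exclusion departs from the all-dosed set; it is better called an exception than a contradiction.
- **That exclusion of deaths is settled.** It is an inference, because the Missing data section does not classify death or failure to wean.
- **That failures would go wholly unseen.** New organ failure is a listed adverse event, adverse-event incidence is compared by arm, and a monitoring board reviews the data. What no section requires by arm is all-cause death and being alive on vasopressors.
- **That counting the stop at death gives the true scale.** At 15% against 5%, with all failures dying, it yields 12.7–24.7% false wins if median death is at 8 h, but 0.7–1.7% at 72 h. It is the less natural reading and carries no weight here.

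**Conclusion.** The gap is real. The sole confirmatory endpoint is undefined for patients who die on vasopressors or never stop them, and the one rule that could be applied selects on a post-randomisation outcome. Bias needs two conditions: failure rates that differ between arms, and failures that are mainly slow weaners. Without either there is none, although with unrelated failures a real difference in failure rates would still be ignored.

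Confidence is high that the rule is absent and low on the size. Failure rates, spread and correlation are all assumed, so the percentages show what is possible, not what is expected. A reader might infer that the primary result is invalid; the documents do not support that. This is a cheap improvement to make before unblinding.

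**What to change.** Amend the SAP before unblinding:

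1. Limit the Missing data exclusion to times that were genuinely not recorded.
2. State that, for the analysis, a vasopressor stop at death is not a discontinuation.
3. Keep all dosed patients in the primary analysis, and record vasopressor stop times after study drug ends, up to a fixed horizon.
4. Make Mann-Whitney the primary test, with deaths on vasopressors ranked worst and patients still on vasopressors at the horizon next.
5. Give time to alive liberation, with death as a competing event, as a sensitivity analysis only. It loses more power: 57–61% at s = 0.75 with 5% failures in both arms.
6. Report failures by arm, split into deaths and patients alive on vasopressors.

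The cost is SAP wording, a few lines of code and perhaps one data-collection instruction. The t-test option is dropped. The test then combines weaning time and failure, so it can favour the arm with fewer failures when latent weaning times are equal: at 15% against 5%, in 4.7–8.3% of trials (ρ 0.5–0.8) or 15–16% (ρ = 0). When failures are equal, some power is lost, as the worst-rank column in step 5 shows.

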### **Interim Analyses**

There will be no interim analysis.

### **Statistical Analytical Issues**

Multiple Comparisons: There will be no adjustment for multiple testing. Results of secondary outcomes and post hoc analyses will therefore be considered exploratory.

### **Post-hoc analyses**

Post-hoc data-driven analyses are allowed after the following are undertaken:

1. Document which analyses were conducted after the results for the primary and secondary outcomes are analysed.
2. Document the rationale for these analyses.
3. Pre-specify their interpretation in the context of the primary and secondary results and their impact on the overall trial conclusions.

